### 1.3 Hypotheses

The hypotheses of this study are:

1. Arginine therapy will decrease time-to-crisis resolution in children with an acute sickle cell vaso-occlusive pain episode compared to placebo.
2. Arginine therapy will lower total parenteral opioid use (mg/kg) compared to placebo.
3. Arginine therapy will improve pain scores compared to placebo.
4. Arginine will have a similar safety profile as placebo.
5. Arginine therapy will improve global arginine bioavailability and mitochondrial activity.

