## 2.8 Results of a single-center, double-blinded, RCT of arginine therapy for children with VOE

A total of 56 children  $> 3$  years old admitted to for VOE were enrolled in this NIH-supported arginine trial (*NHLBI K23 award HL-04386-05*). Mean age was  $13.9 \pm 4$  years (range 3.6–19 years), and 52% were female; 73% had Hb-SS, 18% Hb-SC and 9% carried S- $\beta$  thalassemia. Patients received IV arginine (100mg/kg TID) or placebo during hospitalization. **RESULTS:** Patient characteristics were similar between treatment and placebo groups. Mean time between ED triage and delivery of first randomized study drug dose was  $20.4 \pm 11$  hours, with no difference between the placebo and treatment arm. A significant reduction in opioid use (defined as total opioid use in morphine equivalents during hospitalization in mg/kg) by 54% was observed in the arginine treatment arm compared to placebo (mean  $\pm$  SEM:  $1.9 \pm 0.4$  mg/kg vs.  $4.1 \pm 0.8$  mg/kg;  $p=0.02$ ; Fig 4 A). Pain scores were similar at presentation, but significantly lower at discharge in the arginine arm vs. placebo (Fig 4 B). A clinically relevant trend of decreased hospital length of stay (LOS) by 17 hours favored patients treated with arginine. Total IV opioid use (mg/kg) correlated strongly to LOS ( $r=0.86$ ,  $p < 0.0001$ ), and represents a surrogate biomarker of LOS to evaluate study drug efficacy (Fig 4 C). Rates of ACS, transfusion and AEs were similar in both arms. No drug-related AEs were observed. No significant differences were observed between pre and post therapy liver or renal function, or hematological parameters in the arginine group vs. placebo.

[figure not shown]

Figure 4: Impact of arginine therapy on total opioid use, pain scores, & LOS. **A.** Arginine supplementation (unfilled circles) led to a significant & clinically relevant reduction in total opioid use by 54% over the course of the hospital stay compared to the placebo group (filled circles). The difference remains significant even when the 2 outliers with the largest total opioid use in the placebo arm are excluded from the analysis ( $p=0.04$ ). **B.** Pain scores were significantly lower at discharge in the arginine group compared to placebo by 2 cm. **C.** Correlation between Total Opioid Use (mg/kg) and Length of Hospital Stay (Days).

[figure not shown]

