**Specific Aim 2: To determine the safety profile of IV L-arginine in the treatment of acute VOE in children with SCD.**

Analysis of safety outcomes (acute chest syndrome, requirement of blood transfusion, oxygen use, return visits, and clinical deterioration) will be conducted using Mantel-Haenszel chi-square tests, stratified by clinical center and age group.

Summaries of incidence rates (frequencies and percentages), intensity, and relationship to study of individual Adverse Events (AEs) by System Organ Class and Preferred Term (MedDRA) will be prepared. All AEs beginning after randomization through 14 days or until hospital discharge (whichever comes first) will be included. ED revisits and hospital admissions will be tracked through day 28 after hospital discharge. The occurrence of any adverse event will be considered as a dichotomous outcome and will be compared between groups using a Mantel-Haenszel test, stratified by clinical center and age group. Adverse events will be coded using the latest version of the Medical Dictionary for Regulatory Activities (MedDRA).

**Specific Aim 3: (Exploratory) 3a. To characterize alterations in the arginine metabolome and mitochondrial function in children with SCD and VOE, and evaluate how it is impacted by IV arginine therapy.**

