**Expected:** An event is considered expected if it is known to be associated with the underlying condition or is related to the study intervention and is mentioned in the protocol, informed consent, or other study documents. An event may be expected despite the study subjects clinical state immediately prior to the event.

**Unexpected:** An event is considered unexpected if there are no prior data linking this event with either the condition or intervention under study or an event that occurred unexpectedly in the course of treatment.

Expected complications of opioid administration and sickle cell anemia are summarized in Tables 4 and 5. Other expected adverse events are reactions known to occur with arginine administration, specifically nausea, vomiting, headache, flushing, warmth at the infusion site.

Table 4: Expected Adverse Events Related to Opioid Administration

Anorexia	Headache
Apnea	Hypotension
Biliary tract pressure	Miosis
Blurred vision	Nausea
Bradycardia	Palpitations
Bruising	Pruritus
Cardiac arrest	Rash
Confusion	Respiratory arrest
Cramps	Respiratory depression
Diaphoresis	Sedation
Diplopia	Shock
Dizziness	Tinnitus
Drowsiness	Urinary retention
Euphoria	Urticaria
Flushing	Vomiting

Table 5: Expected Adverse Events Related to Sickle Cell Disease Progression

Angioedema	Leukocytosis
Aplastic crisis	Meningitis
Aplastic crisis/anemia	Metabolic acidosis
Arthralgia	Osteomyelitis
Appendicitis	Pyelonephritis
Bone Infarction	Pain, joint
Cardiomegaly	Pain, long bone
Cerebrovascular accident	Pain, severe abdominal
Cholecystitis, hepatic sequestration	Priapism

*Continued on next page...*

Table 5 – *continued from previous page...*

Cranial nerve palsy	Pulmonary embolism
Decreased kidney function	Pulmonary hypertension
Decreased lung function	Pulmonary parenchymal infiltrates on CXR
Delayed growth/puberty	Pneumonia
Depresses ESR	Rhabdomyolysis
Fever	Renal Failure
Headache	Renal Insufficiency/albuminuria
Hematuria	Renal papillary necrosis
Hemiplegia	Reticulocytosis (10%–20%)
Hemolysis	Retinal disease
Hepato/splenomegaly	Retinal hemorrhage
Hyperplastic bone marrow	Skin ulcers
Hyposthenuria	Splenic sequestration
Hypoxia (PO 2 < 85 mm Hg)	Stroke
Hyperkalemia	Sepsis
Hypotension	Upper respiratory infection
Infection, pneumococcal	Urinary tract infection

**Treatment or Action Taken:** For each adverse event, the site investigator will record whether an intervention was required:

- Medical or surgical procedure

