#### **8.2.4 Data Collection Procedures for Adverse Events**

After patient randomization all adverse events (including serious adverse events) will be recorded according to relatedness, severity, and expectedness, as well as their duration and any treatment prescribed. Any medical condition present at the time of randomization, recorded in the patients baseline history at study entry, which remains unchanged or improves (unless the clinician feels it is clinically relevant), will not be recorded as an adverse event at subsequent evaluations. However, worsening of a medical condition that was present at the time of randomization will be considered a new adverse event and reported.

Abnormal laboratory values that are clinically significant will be recorded as adverse events and the site investigator will assess the severity and relationship to the study. Laboratory values that are abnormal at the time of randomization and that do not worsen will not be recorded as adverse events.

Adverse events will be coded using the MedDRA coding vocabulary. Coding will be done centrally at the Data Coordinating Center as this requires specific training.

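### The only AE-level comparison between arms is any AE, yes or no: a valid net risk, but too insensitive to arginine reactions to support a claim of similar safety

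*Combined protocol and SAP*

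**What the plan says.** Section 5.1 (Specific Aim 2) sets out three layers of safety analysis.

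- **Five named outcomes**, each compared by a Mantel-Haenszel chi-square test stratified by centre and age group: "acute chest syndrome, requirement of blood transfusion, oxygen use, return visits, and clinical deterioration".
- **Summaries of AEs.** Incidence, intensity and "relationship to study of individual Adverse Events (AEs) by System Organ Class and Preferred Term (MedDRA) will be prepared". No comparison is attached, and the text does not say that the summaries are by arm.
- **One AE-level test:** "The occurrence of any adverse event will be considered as a dichotomous outcome and will be compared between groups using a Mantel-Haenszel test", with the same stratification.

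The window is stated as "All AEs beginning after randomization through 14 days or until hospital discharge (whichever comes first) will be included". Cause does not limit what counts. Under section 8.2.4, "After patient randomization all adverse events (including serious adverse events) will be recorded according to relatedness, severity, and expectedness".

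Hypothesis 4 (sections 1.3 and 5) is that arginine and placebo have similar safety profiles; no margin is given. Hypothesis 2 is "Arginine therapy will lower total parenteral opioid use (mg/kg) compared to placebo". On the earlier single-centre trial, section 2.8 reports: "A significant reduction in opioid use (defined as total opioid use in morphine equivalents during hospitalization in mg/kg) by 54% was observed". Table 4 in section 8.2.2 lists 30 expected opioid AEs, and the text before it adds: "Other expected adverse events are reactions known to occur with arginine administration, specifically nausea, vomiting, headache, flushing, warmth at the infusion site".

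**The concern.** All participants are treated with parenteral opioids for acute sickle cell pain, so many may have at least one AE whatever arm they are in. A yes/no variable for any AE cannot register an arginine reaction in someone already counted for opioid sedation or fever.

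Two further features could lower the count on arginine. If the drug spares opioids as Hypothesis 2 expects, some opioid side effects may be avoided. That is an inference: the plan predicts less opioid, not fewer opioid AEs. And because the AE window closes at discharge, a shorter stay also shortens the time at risk.

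The stake is how Hypothesis 4 will be judged. With no margin and one AE-level test, a non-significant p-value is the obvious support for similarity, yet it could arise while drug reactions rise appreciably. None of the five named outcomes is a listed arginine reaction, so their tests do not fill this gap.

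**Working it through.** **Inputs from the documents.** 1:1 allocation (section 4.2); 166 per arm inflated by about 8% (section 5.2): 166 × 1.08 = 179.3, so the stated 180 per arm reproduces. Tests are two-sided (section 5). No significance level is given for the safety tests; 0.05 is assumed.

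**Inputs assumed.** The documents give no AE rates, so all rates below are illustrations. Let p be the risk of at least one opioid or disease AE and r the risk of at least one arginine-type reaction, taken as independent. Then

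any AE = 1 − (1 − p)(1 − r).

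r is set at 5% on placebo and 15% on arginine throughout.

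| Assumed p, placebo → arginine | Any AE, placebo | Any AE, arginine | Difference | Chance of significance |
|---|---|---|---|---|
| 60% → 60% (no sparing) | 1 − 0.40 × 0.95 = 62.0% | 1 − 0.40 × 0.85 = 66.0% | +4.0 points | 12% |
| 60% → 50% (sparing) | 62.0% | 1 − 0.50 × 0.85 = 57.5% | −4.5 points | 14% |
| 40% → 35% (sparing) | 1 − 0.60 × 0.95 = 43.0% | 1 − 0.65 × 0.85 = 44.8% | +1.8 points | 6% |

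Power is by normal approximation. For the first row the mean rate is 0.64, the null standard error is √(2 × 0.64 × 0.36/180) = 0.0506, and 1.96 × 0.0506 = 0.099. Then Φ[(0.040 − 0.099)/0.0506] = Φ(−1.17) = 0.12.

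**Dilution and offset.** The first row has no sparing at all, and power is still 12%, so dilution by a common background is enough to blunt the test. Sparing mainly changes the direction of the estimate. If arginine causes a reaction in a fraction q and there are no such reactions on placebo, the any-AE rates are equal when opioid and disease AEs are multiplied by

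RR = [1 − (1 − p)/(1 − q)]/p.

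For q = 10% this is 0.833, 0.926 and 0.972 at p = 40%, 60% and 80%: relative falls of 17%, 7% and 3%.

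**Check with the planned test.** 2,000 trials per scenario were simulated with Mantel-Haenszel over 20 strata (10 sites × 2 age groups), p = 60%, q = 15% and a 2% background of arginine-type reactions. Significant harm on any AE appeared in 22% of trials with no sparing, 3% with 10% fewer opioid-type AEs, and 0.2% with 20% fewer. In the last case 12% of trials significantly favoured arginine.

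**What a null result would exclude.** The 95% half-width for the no-sparing row is 1.96 × √[(0.62 × 0.38 + 0.66 × 0.34)/180] = 0.099, about 10 points. For background rates of 40% to 80% it is about 8 to 10 points.

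**Does splitting by reaction cure it?** Only partly. A reaction at 5% v 15% with nothing else mixed in has 89% power. But nausea, vomiting, headache and flushing, four of the five listed arginine reactions, are also in Table 4. Suppose opioid nausea affects 30% and arginine causes nausea in 10%. Without sparing, observed nausea is 30% v 1 − 0.70 × 0.90 = 37%, with 29% power. If opioid nausea falls to 25%, it is 30% v 1 − 0.75 × 0.90 = 32.5%, with about 8% power.

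**The case against.** The strongest reply is that safety does not rest on any AE alone. Five clinically important outcomes have their own stratified tests. Return visits and admissions are among them, so part of what would qualify as an SAE through hospitalisation is compared. The planned tables by organ class and preferred term, with intensity and relationship, could show an excess of flushing or vomiting whatever the net test reads. The medical monitor assesses every SAE, and the DSMB reviews all AEs. All of this stands, and it limits the point to the absence of planned between-arm estimates.

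The rates are also assumptions. Section 2.8 reports no drug-related AEs in the earlier trial, so a 10-point excess has no support in the text. Events before randomisation are baseline conditions (section 8.2.3), and those that do not worsen are not recorded (section 8.2.4), so some opioid effects never enter the count. With a low background and frequent reactions the test can work: at 30% background, 20% caused and no sparing, any AE is 30% v 1 − 0.70 × 0.80 = 44%, with 79% power.

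A reader might infer that the test is biased, because arginine's reactions can only become more frequent and must cancel against fewer opioid AEs. The documents do not support that. Given the overlap with Table 4, the recorded frequency of four of the five reactions could fall if opioid use falls. Cancellation depends on rates that nobody has stated. And an unbiased estimate of net risk is not biased because it answers a different question.

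**Conclusion.** The point holds as one of sensitivity and interpretation. Any AE is a legitimate net measure, but under the rates illustrated it has roughly a 6% to 14% chance of significance when arginine-type reactions triple from 5% to 15%, and the estimate may favour arginine. With a half-width of 8 to 10 points and no margin, a non-significant result does not show a similar safety profile. These figures rest on assumed, independent component rates, 180 per arm and a two-sided 0.05 level; the actual loss of sensitivity cannot be known from the documents.

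Two stronger conclusions should not be drawn. One is that the plan has no other comparative safety analysis: it has five named tests. The other is that the earlier trial, with 54% less opioid use and similar AE rates in both arms, demonstrates masking: those results are equally compatible with no excess of drug reactions.

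This is a cheap improvement to the analysis plan and of lower priority than a correction to an erroneous analysis.

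**What to change.** Keep any AE as the net summary. In section 5.1, add stratified Mantel-Haenszel risk differences with 95% confidence intervals for:

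- (a) any SAE;
- (b) any severe AE;
- (c) any AE rated possibly or probably related to study treatment.

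Report each arginine reaction listed in section 8.2.2 by arm in the same way. State beside those rows that nausea, vomiting, headache and flushing are also expected opioid AEs, so their differences are net effects with low power where the background is high. State also that blinded relatedness ratings may take in opioid effects in either arm.

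Base the conclusion on Hypothesis 4 on these intervals together with the five named outcomes and any AE, not on the absence of significance in one test.

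The cost is a paragraph in the analysis plan and a few table rows; seriousness, severity, relatedness and preferred term are already recorded. The downside is several more safety comparisons, which should be read descriptively with no multiplicity claim.

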## 5.2 Sample Size Calculations and Statistical Power

Based on a previous small trial, the difference between arginine and placebo groups is approximately 0.7 days (length of stay, which parallels time to crisis resolution). A Type I error bound of 0.05 (alpha) for the primary hypothesis will be used and it will be assumed that age is not informative of outcome (a conservative bound for sample size). A simulation-based approach is used to determine the sample size required to detect a difference (shift in distribution) of 0.7 days with 85% power. In order to simulate placebo outcomes, time-to-crisis resolution data from the MAGiC trial (both arms combined, as the treatment effect did not reach statistical significance) was used. For the arginine arm, outcomes were simulated from the same distribution, shifted down by 0.7 days. 5,000 trials were simulated. This process resulted in a required sample size of 166 per arm. Accounting for withdrawal (~1%), interim efficacy monitoring (inflation of 2%), and crossover/non-adherence (3%, for example, arginine subjects who do not receive a sufficient amount of study drug) results in an overall inflation of about 8% or a total of 180 per arm. Prior to the first interim analysis (after approximately 100 subjects), the DCC and CCC principal investigators, along with the DSMB, will review, blinded to by-treatment results, summaries of the outcome distribution (mean, median, IQR with both arms combined – to compare with MAGiC data), withdrawal rate, and non-adherence rates and may adjust the target sample size accordingly, as funding allows.

Given a total sample size of 180 per arm, the effect size that will be detectable in subgroup analyses of the primary outcome, for example, a differential treatment effect based on gender or hydroxyurea use will also be reported. With 85% power, it will be possible to detect an effect size (difference in differences) of about 1.3 days, or approximately 1.9 times the main treatment effect size for which the study is powered. With 80% power, it will be possible to detect an effect size of 1.2, or 1.7 times the main treatment effect size.

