## 5 Data Analysis

All analyses will be undertaken by the intention-to-treat (ITT) principle. Patients who drop out (discontinue study drug) will be followed and included in the ITT analysis. All statistical tests of hypotheses will be two-sided.

The hypotheses of this study are:

1. Arginine therapy will decrease time-to-crisis resolution in children with an acute sickle cell vaso-occlusive pain episode compared to placebo.

2. Arginine therapy will lower total parenteral opioid use (mg/kg) compared to placebo.
3. Arginine therapy will improve pain scores compared to placebo.
4. Arginine will have similar safety profile than placebo.
5. Arginine therapy will improve global arginine bioavailability and mitochondrial activity.

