## 5.3 Subgroups

The formal subgroups specified for this trial will be age group, hydroxyurea use, and sex. The interaction between assigned treatment and each subgroup factor in a linear model, at a significance level of 0.05/3 will also be tested. The model will include a main effect for treatment, a main effect for subgroup factor, and an interaction between the subgroup factor and treatment. Secondary outcomes in similar models will also be observed.

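### The subgroup detectable effect in Section 5.2 (1.3 days at 85% power) fits a 0.05 test, but Section 5.3 tests each interaction at 0.05/3, where about 1.5 days is needed

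*Combined protocol and SAP*

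**What the plan says.** Section 5.2 sizes the trial to "detect a difference (shift in distribution) of 0.7 days with 85% power", and reports: "This process resulted in a required sample size of 166 per arm". The only significance level in that section belongs to the primary test: "A Type I error bound of 0.05 (alpha) for the primary hypothesis will be used". After inflation to 180 per arm, it turns to interactions, with gender and hydroxyurea use as examples: "With 85% power, it will be possible to detect an effect size (difference in differences) of about 1.3 days, or approximately 1.9 times" the main effect. It adds: "With 80% power, it will be possible to detect an effect size of 1.2, or 1.7 times the main treatment effect size".

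Section 5.3 defines the tests to which those figures apply. "The formal subgroups specified for this trial will be age group, hydroxyurea use, and sex", and "The interaction between assigned treatment and each subgroup factor in a linear model, at a significance level of 0.05/3 will also be tested".

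The introduction to Section 5 settles sidedness: "All statistical tests of hypotheses will be two-sided".

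**The concern.** Both examples in Section 5.2 are among the three formal subgroup factors of Section 5.3, so the two sections describe the same tests. A Bonferroni-type level of 0.05/3 needs a larger effect for the same power than 0.05 does. Section 5.2 does not say that its figures allow for this, and its multiple of 1.9 is close to what an unadjusted test would give.

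What is at stake is how the subgroup results are read. A reader who sees a null interaction by age group, sex or hydroxyurea use would credit the test with 85% power at 1.3 days. If the true power is nearer 70%, a null result rules out less than the plan implies.

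**Working it through.** **Inputs from the plan:** main effect 0.7 days, 85% power, two-sided 0.05, 166 per arm (Sections 5 and 5.2); 180 per arm for the subgroup figures (5.2); equal allocation (4.2); 0.05/3 for each interaction in a linear model (5.3).

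**Assumptions:** subgroups split evenly, giving 90 patients per treatment-by-subgroup cell. The SD is not stated, so it is backed out in two ways: treating the primary test as a normal-theory test, or giving the rank test its normal-data efficiency of 3/π = 0.955.

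**Normal quantiles:** 1.960 for two-sided 0.05; 2.394 for two-sided 0.05/3; 1.036 for 85% power; 0.842 for 80% power.

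**Step 1, implied SD.** The main-effect SE is 0.7/(1.960 + 1.036) = 0.2336. The SD is 0.2336 × √(166/2) = 2.13 days, or 2.13 × √0.955 = 2.08 days with the rank-efficiency adjustment.

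**Step 2, interaction SE.** SE = SD × √(4/90) = 0.4487 (SD 2.13) or 0.4385 (SD 2.08).

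**Step 3, detectable effect** = SE × (z for alpha + z for power). Each range runs from SD 2.08 to SD 2.13.

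| Two-sided level | 85% power | 80% power |
|---|---|---|
| Printed in 5.2 | 1.3 days (1.9 times) | 1.2 days (1.7 times) |
| 0.05 | 1.31–1.34 days (1.88–1.92 times) | 1.23–1.26 days (1.75–1.80 times) |
| 0.05/3 | 1.50–1.54 days (about 2.2 times) | 1.42–1.45 days (2.0–2.1 times) |

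The 0.05 row reproduces the printed 85% figure; the 0.05/3 row does not. The multiple can also be checked without an SD. With an even split and equal efficiency, an interaction has twice the main-effect SE, so at the same level and power the multiple is 2 × √(166/180) = 1.92. At 0.05/3 it is 1.92 × 1.145 = 2.20.

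**Step 4, power at the printed effects under 0.05/3.** Power = Φ(effect/SE − 2.394).

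- 1.3 days: Φ(1.3/0.4487 − 2.394) = 69.3%; with SE 0.4385, 71.6%.
- 1.2 days: 61.0% and 63.4%.

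**Step 5, the change of level alone.** This needs neither an SD nor a split.

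- A test with 85% power at 0.05 has Φ(1.960 + 1.036 − 2.394) = 72.7% at 0.05/3.
- A test with 80% power at 0.05 has Φ(1.960 + 0.842 − 2.394) = 65.8%.
- The detectable effect grows by 3.430/2.996 = 1.145 at 85% power and 3.236/2.802 = 1.155 at 80%.

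**Step 6, could 1.3 days already allow for 0.05/3?** With an even split the SD would have to be 1.3/3.430/√(4/90) = 1.80 days. Against 2.13, that is a rank-test efficiency of (1.80/2.13)² = 0.71, below the lower bound of 0.864 for a shift. At that bound, 0.05/3 still requires 1.43 days. Reading the printed 1.3 as a rounded 1.35 would still need an efficiency of 0.77.

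**Simulation check** (normal data, least-squares interaction, 90 per cell, 20,000 runs, effect 1.3 days): SD 2.08 gives 84.2% power at 0.05 and 71.4% at 0.05/3; SD 2.13 gives 82.3% and 68.8%.

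**The case against.** The best reply is that Section 5.2 is under-specified rather than wrong. It attaches 0.05 only to the primary hypothesis and gives no level for the subgroup figures, so the two sections do not contradict each other on their face. That is fair, and it is why the 0.05 reading is called an inference. It does not help the figure, because Step 6 shows that the 0.05/3 reading does not work with the plan's own inputs. One-sided testing is excluded by Section 5, and even one-sided 0.05/3 needs 1.42 days (SD 2.13).

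Four narrower points stand:

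- **The exact day values depend on the data's shape.** If time to resolution is right-skewed, the rank test can be more efficient than the linear model and the implied SD is larger. At an illustrative efficiency of 1.5, the interaction test needs 1.65 days at 0.05 and 1.89 at 0.05/3. The printed 1.3 would then fit neither level, and 1.5 would be too low as well.
- **The even split is the favourable case.** With SD 2.13 at 0.05/3, a 70/30 split needs 1.68 days and an 80/20 split 1.92. All twelve children in the pharmacokinetic study in Section 2.7 were on hydroxyurea, so an even split on that factor cannot be presumed.
- **The 69% end includes some rounding.** With SD 2.13, power at 1.3 days is already 82.6% at 0.05. The change of level alone takes 85% to 72.7%.
- **The 80% figure and the multiples add little.** An SE taken from the printed 1.3 gives 1.22 days at 80% power and 0.05, so the printed 1.2 may be rounding only. The multiples may simply be rounded days over 0.7 (1.3/0.7 = 1.86; 1.2/0.7 = 1.71).

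The figures are also illustrative and drive no decision rule, which limits the consequence but does not make the stated power right.

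**Conclusion.** The concern holds. The printed 1.3 days at 85% power matches an unadjusted two-sided 0.05 test and cannot be reconciled with the 0.05/3 level set for the same tests. At 0.05/3, with 180 per arm and an even split, about 1.5 days is needed for 85% power. Power is about 69–73% at 1.3 days and 61–66% at 1.2 days, and lower if the split is uneven. The upper ends, 73% and 66%, take each printed effect as exactly right at 0.05.

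Confidence is high for the mismatch of level and moderate for the day values, because the level, SD and split behind the printed figures are inferred. The sample size, the primary analysis and the validity of the interaction tests are not affected.

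**What to change.** Recompute the Section 5.2 subgroup figures at two-sided 0.05/3 and print the SD and subgroup split used. By back-calculation with an even split, expect about 1.5 days (about 2.2 times the main effect) at 85% power and about 1.42–1.45 days (2.0–2.1 times) at 80%. The coordinating centre holds the data behind its simulation and can replace these with exact values, ideally using a realistic split for each of the three factors.

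At minimum, label the present figures as applying to an unadjusted two-sided 0.05 test with an even split, and reconfirm the 80% figure, for which back-calculation at 0.05 gives 1.23–1.26 days.

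The cost is protocol and SAP wording only. The stated sensitivity of the subgroup tests becomes somewhat less favourable; nothing changes in enrolment or the primary analysis.

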## 2.7 R34 pharmacokinetic study

Twelve children with SCD hospitalized for VOE were randomized to treatment utilizing one of 3 dosing schemes of L-arginine: 1) 100 mg/kg IV three times/day (TID; n=4); 2) loading dose (200 mg/kg) then 100 mg/kg TID (n=4); or 3) loading dose (200mg/kg) followed by continuous infusion (300mg/kg/day) until discharge (n=4). Platelet rich plasma was isolated and stored at baseline and discharge for each subject and mitochondrial electron transport complex activities measured (Fig 3 on the following page).

**Results:** Mean age was 14±3 years, 75% had Hb-SS, 67% were male and all were on Hydroxyurea (HU). Compared to SCD patients in steady state, all subjects with VOE had a significantly decreased complex V activity (Fig 3 A). Notably, complex V activity was increased at discharge in children with VOE treated with Arginine in all 3 dosing schemes. However, the increase in complex V activity was greatest with loading dose arms compared to

[figure not shown]

Figure 3: Arginine impact on mitochondrial activity

standard dose (Fig 3 B). While complex IV and citrate synthase activities were not changed in platelets from subjects with VOE vs. steady state (*data not shown*), the activities of these enzymes were also significantly increased in VOE subjects after Arginine treatment (loading dose then continuous infusion, Fig 3 C–D). These changes with arginine are not due to increased mitochondrial number as quantification of mitochondrial DNA before and after arginine were similar (Fig 3 E). IV Arginine significantly decreased levels of protein carbonyls in the platelet-rich plasma, suggesting a decrease in oxidative stress (Fig 3 F). **Conclusion:** Promising reports of oral and IV arginine use for complications of mitochondrial encephalomyopathy, lactic acidosis and stroke-like episodes (MELAS) have been described. Our data demonstrate for the first time that arginine supplementation increases mitochondrial activity in SCD/VOE, which may mechanistically contribute to decreased pain and less opioid requirement after IV arginine, as well as have further implications for improved metabolism and oxidative signaling in these patients. Although this pilot work did not include a placebo arm, the significant dose-dependent effect suggests a differential effect of L-arginine in SCD.

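### The subgroup detectable effect in section 5.2 (about 1.3 days at 85% power) assumes an even split and alpha 0.05, but section 5.3 tests each interaction at 0.05/3, so it is too favourable for all three formal factors

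*Combined protocol and SAP*

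**What the plan says.** Section 5.2 sizes the trial to "detect a difference (shift in distribution) of 0.7 days with 85% power" and arrives at 166 per arm, inflated to 180. On the error rate it says: "A Type I error bound of 0.05 (alpha) for the primary hypothesis will be used". For subgroup analyses with 180 per arm it then states: "With 85% power, it will be possible to detect an effect size (difference in differences) of about 1.3 days", which it describes as roughly 1.9 times the main effect. It adds 1.2 days (1.7 times) at 80% power. Gender and hydroxyurea use are its examples. It gives no subgroup share and no significance level for these figures.

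Section 5.3 says: "The formal subgroups specified for this trial will be age group, hydroxyurea use, and sex". Each treatment-by-factor interaction is tested "in a linear model, at a significance level of 0.05/3". Section 5 adds: "All statistical tests of hypotheses will be two-sided".

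Section 4.2 stratifies randomization by clinical center and age group (below 12 against 12 and over). Hydroxyurea use and sex are not stratification factors, and no quota is set for any of the three.

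**The concern.** A single detectable interaction is offered for factors whose level sizes may differ widely, and it is not tied to the significance level at which the interactions will be tested. An even split gives the smallest standard error for an interaction, so a figure computed that way is a best case. A stricter significance level raises the detectable effect again.

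What is at stake is the stated sensitivity of the trial's three formal subgroup tests. Anyone setting a non-significant hydroxyurea, age or sex interaction against section 5.2 would credit the test with 85% power for a 1.3-day differential effect that the written design does not deliver.

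**Working it through.** **Inputs.** From section 5.2: main effect 0.7 days, 166 per arm, 85% power, alpha 0.05, and 180 per arm (N = 360) for the subgroup figure. From section 5.3: alpha 0.05/3 = 0.0167 per interaction. Tests are two-sided (section 5) and allocation is equal (section 4.2). The SD is not stated, so it is back-solved on a normal-equivalent basis, which is an assumption.

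**Step 1: implied SD.** SD = 0.7 / [√(2/166) × (1.960 + 1.036)] = 2.13 days.

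**Step 2: reproduce the printed figure.** With share p in one subgroup level and 1:1 treatment within each level, the interaction SE is SD × √(4 / (N p(1−p))). At p = 0.5 and N = 360 this is 2.128 × √(4/90) = 0.449 days.
- 85% power, alpha 0.05: 0.449 × (1.960 + 1.036) = 1.34 days, or 1.92 × 0.7. Equivalently, 2 × 0.7 × √(166/180) = 1.34. This matches the printed 1.3 and 1.9.
- 80% power, alpha 0.05: 0.449 × (1.960 + 0.842) = 1.26 days, slightly above the printed 1.2.
- Alternatives fit the 85% figure less well: N = 332 gives 1.40 days, and alpha 0.05/3 gives 1.54 days. One-sided 0.05 gives 1.20 days and contradicts section 5.

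So the printed value corresponds to an even split and two-sided 0.05.

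**Step 3: use the planned level.** The critical value for 0.05/3 is 2.394. At 50/50:
- power at exactly 1.3 days: Φ(1.3/0.449 − 2.394) = 69.3%;
- power at the unrounded 1.344 days: Φ(2.996 − 2.394) = 72.7%;
- detectable effect at 85% power: 0.449 × (2.394 + 1.036) = 1.54 days, or 2.2 × 0.7;
- detectable effect at 80% power: 0.449 × (2.394 + 0.842) = 1.45 days.

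**Step 4: uneven splits.** An uneven split divides the effect-to-SE ratio at 50/50 by 1/(2√(p(1−p))). Power below is for 1.344 days.

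| Split (assumed) | 2√(p(1−p)) | Power, 0.05 | Loss from split alone (points) | Power, 0.05/3 | Detectable at 85%, 0.05/3 (days) |
|---|---|---|---|---|---|
| 50/50 | 1.000 | 85.0% | 0 | 72.7% | 1.54 |
| 65/35 | 0.954 | 81.6% | 3.4 | 67.9% | 1.61 |
| 68/32 | 0.933 | 79.8% | 5.2 | 65.6% | 1.65 |
| 75/25 | 0.866 | 73.7% | 11.3 | 58.0% | 1.78 |
| 80/20 | 0.800 | 66.9% | 18.1 | 50.1% | 1.92 |
| 90/10 | 0.600 | 43.6% | 41.4 | 27.6% | 2.57 |

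**Step 5: what the documents say about shares.**
- Hydroxyurea: the only figure is 12 users among 12 children in the pharmacokinetic study (section 2.7). The exact 95% lower bound is 0.025^(1/12) = 74%, if those children are treated as a random sample of this trial's population.
- Age: the earlier IV trial had mean 13.9 ± 4 years (section 2.8) and the pharmacokinetic study 14 ± 3 (section 2.7). Reading the ± as an SD and assuming normality, the share below 12 is Φ(−1.9/4) = 32% and Φ(−2/3) = 25%. The oral trial (section 2.9) had mean 10.6 years, which points the other way.
- Sex: 48% male (52% female) in section 2.8, 67% male in section 2.7 and 38% male in section 2.9. At 0.05 a 62/38 split costs about 2 points and 67/33 about 4.5.

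**The case against.** **The shares are not in the documents.** This stands. Twelve children in a pharmacokinetic study do not fix hydroxyurea use at ten sites. The exclusion for new use or a dose change within 3 months (section 1.6) removes users only, which would tend to lower the share. At 65% use the split costs only about 3 points. The age estimates rest on normality in two small studies, and the oral trial disagrees, although it enrolled Nigerian children and this trial enrols in the United States. The split losses are therefore an assumed range.

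**The calibration is indirect.** The sizing came from a simulation on data from an earlier magnesium trial, and the primary test is rank-based, while the interaction test is a linear model. The back-solved SD may be off. The significance-level point survives this. Under a pure shift, the large-sample efficiency of the Wilcoxon rank test relative to the t-test is at least 0.864, so the SD is at least 2.13 × √0.864 = 1.98 days. The detectable effect at 50/50 and 0.05/3 is then still 1.54 × √0.864 = 1.43 days. For 1.3 days to hold at 0.05/3 the SD would have to be 1.80, which would give the main comparison about 94% power, not 85%. The even-split inference is less tightly pinned: at that extreme SD and alpha 0.05, the 50/50 value is 1.25 days, so 1.3 would tolerate about 64/36.

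**Readings that go too far.** A reader might infer that 1.3 days is right for sex and wrong only for hydroxyurea and age. It is not: at 0.05/3 it fails for sex as well, and sex is not shown to be exactly even. A reader might also infer that the plan's data establish 80–90% hydroxyurea use. They do not.

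**The consequence is limited.** Also fair. Subgroup power drives neither the sample size nor a stopping rule, and nothing in the plan says that a null interaction will be taken to exclude 1.3 days.

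**Conclusion.** The concern holds. Section 5.2's subgroup figures are a best case on two unstated assumptions, and one of them, alpha 0.05, conflicts with section 5.3. That mismatch is the firmer part: power at the printed effect is about 69–73% instead of 85% for every formal factor, even at an even split. Uneven splits add an uncertain further loss. With both effects combined, power is about 66% at 68/32 and 50% at 80/20. Hydroxyurea is a poor example for an even-split figure, because the design does nothing to balance its levels and the one small sample in the documents had no non-users.

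The numbers rest on an SD of 2.13 days back-solved from the plan's sizing, equal variance across cells, 1:1 treatment within each level, and the assumed splits. The finding concerns reported sensitivity only. It does not show that the primary comparison is underpowered.

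**What to change.** In section 5.2:
- State the split and the significance level behind the subgroup figures.
- Replace the single value with effects detectable at 85% power and the planned 0.05/3, over splits labelled as assumed: about 1.54 days at 50/50, 1.65 at 68/32, 1.78 at 75/25, 1.92 at 80/20 and 2.57 at 90/10. If an 80% figure is kept, restate it on the same basis (1.45 days at 50/50). The study team holds the simulation data and can replace the back-solved SD.
- Do not keep 1.3 days for sex, and do not use hydroxyurea as an example of the even-split figure.
- Update the figures with the observed shares at the blinded review already planned at about 100 subjects.

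The cost is a short rewrite of one paragraph and a less favourable stated sensitivity. No patients, data or changes to the primary analysis or enrolment are needed.
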